11.3 Data Analyses

The MTD is defined as the largest dose for which fewer than 33% of patients experience a DLT. The MTD will be estimated by the highest alvocidib dose for which the empirical incidence of DLT during Cycle 1 was less than 33% in combination with 7+3.

Incidence rates of treatment-emergent adverse events will be summarized within treatment group at the MedDRA preferred term and primary system organ class levels. Similar summaries will be made for subsets of AEs such as (1) those judged by the Investigator to be related to study treatment, and (2) serious adverse events (SAEs).

Other routine safety assessments (eg, clinical laboratory parameters and vital signs) will be summarized by standard deviation, median, minimum and maximum observed values and changes from baseline values.

The multivariate analysis and risk score prediction model by Montesinos and colleagues [38] will be used to assess the potential for development of TLS (see [Appendix F](#)).

11.3.1 Demographics and Baseline Characteristics

Demographics and baseline characteristics will be summarized by alvocidib dose level and overall using descriptive statistics and confidence intervals.

11.3.2 Efficacy Analyses

Objective response to treatment will be determined using the remission definitions detailed in the 2017 European LeukemiaNet Recommendations in AML [10] after Induction/Reinduction (for those patients not achieving a CR after Cycle 1) (see [Appendix E](#)).

- CR_{MRD-} = CR without MRD
- CR = Complete Remission (including patients with morphologic CR who are MRD+ and cytogenetic and/or molecular marker positive)
- CR_i = CR with incomplete hematologic recovery
- MLFS = Morphologic leukemia-free state
- PR = Partial Remission
- SD = Stable Disease
- PD = Progressive Disease

The numbers of overall complete remissions (patients with a best objective response of CR_{MRD}, CR, CR_i or MLFS), and overall remissions (patients with a best objective response of CR_{MRD}, CR, CR_i, MLFS or PR) will be summarized by observed rates and estimated 95% CIs. If there are sufficient numbers of patients achieving remissions for an analysis to be informative, logistic regression will be used to model the probability of achieving a remission as a function of the total alvocidib daily dose level (bolus dose amount + infusion dose amount) and biomarker prediction endpoints (eg, MRD).

Kaplan-Meier time-to-event analyses will be conducted on overall survival, relapse-free survival and duration of remission. Mortality (all causes) at 30 and 60 days will also be calculated. Cox proportional hazards models will be fit to these time-to-event endpoints with the total alvocidib daily dose level (bolus dose amount + infusion dose amount) and biomarker prediction endpoints (eg, MRD) serving as independent variables in the model.

Additional exploratory analyses may be performed to assist the sponsor in planning future studies.

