1.1.2 Newly Diagnosed and Previously Untreated AML

Genetic abnormalities are the prevailing prognostic factors in determining response to treatment [10]. A number of studies have investigated the relative contribution of genetic and clinical variables to prediction of event-free survival (EFS) and overall survival (OS). Results from conventional cytogenetics and from certain mutational screenings are now routinely employed in clinical practice following recommendations by the European LeukemiaNet group in 2017.

The presence of specific genomic aberrations accounts for about two thirds of variability in predicting disease response in patients with AML; the remaining third is a combination of demographic, clinical, and treatment variables [10]. Advances have been made in incorporating these key data into models to aid physicians in predicting whether a given set of covariates conveys a longer remission or life expectancy compared to another patient with a different set of covariates. However, the accuracy of these models in correctly pinpointing the likelihood of response hovers around 75%. Along with the need to identify additional pretreatment prognostic factors that can address the remaining quarter of patients in whom response is likely, there is hope that evaluation of post-treatment events such as the presence of minimal residual disease (MRD) will further boost the percentage of likely responders.

There are different methods one can use to assess the presence of MRD, with each methodology varying in the proportion of patients to whom it can be applied and in its sensitivity to detect MRD. By integrating the evaluation of baseline factors together with the assessment of MRD, risk assessment should improve to better direct post-remission therapy.

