5.2.5 Induction, Day 14 (± 3 Days)

- Collect peripheral blood samples and perform a bone marrow biopsy on Day 14 (± 3 days), unless medically contraindicated, for disease assessment including MRD and other potential biomarkers. Central laboratory assessment of MRD is to be done for disease assessment and treatment guidance.
 - Patients with **no** evidence of residual leukemia will be monitored weekly (as in [Section 5.2.4](#)) until hematologic recovery (go to [Section 5.2.6](#))
 - Patients **with** evidence of residual leukemia ($>5\%$ bone marrow blasts plus $>10\%$ cellularity) may be eligible for a second Induction cycle (or ‘Reinduction’) with alvocidib and 5+2 at the discretion of the Investigator (go to [Section 5.3](#)).
- Assess for AEs
- Record only those medications (prescription, nonprescription, nutritional supplements) administered in conjunction with an AE.

5.2.6 Induction – At Hematologic Recovery or Day 50 (± 3 days), Whichever Occurs First

- Patients will undergo response assessment including MRD via peripheral blood and bone marrow biopsy samples collected at the time of hematologic recovery (ie, absolute neutrophil count [ANC] $>1000/\mu\text{L}$ and platelet count $>100,000/\mu\text{L}$) or Day 50 [± 3 days], counted from Day 1 of Induction therapy, whichever occurs first. These same samples will also be used for assessment of other potential biomarkers. Central laboratory assessment of MRD is to be done for disease assessment and treatment guidance. If the bone marrow biopsy and/or aspirate is nonproductive or not diagnostic, the procedure must be repeated within 7-10 days.
- Additional bone marrow assessments may be obtained per Investigator discretion.
- Assess for AEs, including tumor lysis clinical symptoms
- Record only those medications (prescription, nonprescription, nutritional supplements) administered in conjunction with an AE.

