5.4.5 Consolidation – Response Assessment

- After Consolidation cycles 2 and 4, patients will undergo response assessments including MRD via peripheral blood and bone marrow biopsy samples collected at the time of hematologic recovery (ie, ANC >1000/ μ L and platelet count >100,000/ μ L). These same samples will also be used for assessment of other potential biomarkers. Central laboratory assessment of MRD is to be done for disease assessment and treatment guidance. If the bone marrow biopsy and/or aspirate is nonproductive or not diagnostic, the procedure must be repeated within 7-10 days.
- Additional bone marrow samples may be requested at the discretion of the Investigator.
- Assess for AEs
- Record only those medications (prescription, nonprescription, nutritional supplements) administered in conjunction with an AE.

5.4.6 Consolidation – Cycles 2 through 4

Patients who plan to receive chemotherapy-based consolidation should get a minimum of two cycles of Consolidation up to a maximum of four cycles. Patients proceeding to stem cell transplant for Consolidation should get one cycle of Consolidation, if possible, to ensure disease stability while transplant plans are being made.

Each cycle will include the assessments listed in Section 5.4.1 through Section 5.4.5.

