APPENDIX E – RESPONSE CRITERIA (2017 EUROPEAN LEUKEMIANET RECOMMENDATIONS)

Category	Definition	Comment
Response		
• CR without minimal residual disease (CR _{MRD})	If studied pre-treatment, CR with negativity for a genetic marker by real-time quantitative polymerase chain reaction (RT-qPCR), or CR with negativity by multi-color flow cytometry	Sensitivities vary by marker tested, and by method used; therefore, test used and sensitivity of the assay should be reported; analyses should be done in experienced laboratories (centralized diagnostics)
• Complete remission (CR)	Bone marrow blasts <5%; absence of circulating blasts and blasts with Auer rods; absence of extramedullary disease; absolute neutrophil count $\geq 1.0 \times 10^9/L$ (1,000/ μ L); platelet count $\geq 100 \times 10^9/L$ (100,000/ μ L)	MRD positive or unknown*
• CR with incomplete hematologic recovery (CR _i)	All CR criteria except for residual neutropenia [$<1.0 \times 10^9/L$ (1,000/ μ L)] or thrombocytopenia [$<100 \times 10^9/L$ (100,000/ μ L)]	
• Morphologic leukemia-free state (MLFS)	Bone marrow blasts <5%; absence of blasts with Auer rods; absence of extramedullary disease; no hematologic recovery required	Marrow should not merely be “aplastic”; at least 200 cells should be enumerated or cellularity should be at least 10%
• Partial remission (PR)	All hematologic criteria of CR; decrease of bone marrow blast percentage to 5% to 25%; and decrease of pretreatment bone marrow blast percentage by at least 50%	Especially important in the context of phase 1-2 clinical trials

*Including patients with morphologic CR who are MRD+ and cytogenetic and/or molecular marker positive.

2017 EUROPEAN LEUKEMIANET RECOMMENDATIONS (Cont)

Category	Definition	Comment
Treatment failure		
• Primary refractory disease	No CR or CR _i after 2 courses of intensive induction treatment; excluding patients with death in aplasia or death due to indeterminate cause	Regimens containing higher doses of cytarabine (see Table 8) are generally considered as the best option for patients not responding to a first cycle of 7+3; the likelihood of responding to such regimens is lower after failure of a first
• Death in aplasia	Deaths occurring ≥ 7 days following completion of initial treatment while cytopenic; with an aplastic or hypoplastic bone marrow obtained within 7 days of death, without evidence of persistent leukemia	

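### Protocol 11.3.2 uses post-treatment MRD as a predictor of remission, which is circular at the response assessment, and as a fixed Cox covariate for survival, which can build in immortal time; the SAP drops these models without withdrawing them.

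*Protocol*

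**What the plan says.** **The protocol's models.** Section 11.3.2 states, on condition of enough remissions, that "logistic regression will be used to model the probability of achieving a remission as a function of the total alvocidib daily dose level" together with biomarker endpoints, for which MRD is the example given. It also states that "Kaplan-Meier time-to-event analyses will be conducted on overall survival, relapse-free survival and duration of remission", and that Cox models will be fitted to these endpoints with "biomarker prediction endpoints (eg, MRD) serving as independent variables in the model". The Cox models carry no such condition. Baseline biomarkers have their own section and logistic model in 11.3.3.

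**When MRD is measured.** Section 1.1.2 classes MRD as a post-treatment matter: "evaluation of post-treatment events such as the presence of minimal residual disease (MRD". The scheduled MRD assessments all follow first dose:
- Day 14 (5.2.5): marrow and blood are taken "unless medically contraindicated, for disease assessment including MRD and other potential biomarkers".
- Recovery or Day 50 (5.2.6): "Patients will undergo response assessment including MRD via peripheral blood and bone marrow biopsy samples collected at the time of hematologic recovery". Section 5.3.1 does the same at recovery or Day 60 after Reinduction.
- Consolidation (5.4.5): "After Consolidation cycles 2 and 4, patients will undergo response assessments including MRD".
- End of Study (5.5), if no marrow was taken in the preceding 30 days.

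**MRD inside the response.** Section 11.3.2 lists CR without MRD as a response category and counts it in both remission totals. Appendix E defines it as CR plus a negative MRD test.

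**The SAP.** OS runs from first dose in all patients (7.8.3). RFS and CR duration run from the date of CR (7.8.4, 7.8.5). The logistic and ROC analyses use baseline MCL-1 dependence only (7.8.1, 7.9). No Cox model is specified, and Table 3 plans no table with MRD as a covariate.

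**The concern.** Two problems follow from putting a post-treatment measurement on the predictor side.

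First, MRD at the response assessment comes from the same samples as the response call and helps to define it. A model of remission on that variable partly predicts the outcome from itself.

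Second, OS starts at first dose, while MRD status becomes known later. A patient can be MRD-negative only after surviving to the sample. If early deaths are placed in the comparison group, MRD-negative patients appear to live longer even when MRD carries no information.

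MRD is an exploratory objective, and testing the feasibility of dual-method MRD is a stated purpose of the expansion at the MTD. Section 11.3.2 also foresees exploratory analyses to help plan later studies. An inflated association between MRD and outcome could carry into those plans.

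**Working it through.** The plan gives no effect size, event count or power for these models, so it has no figure of its own to reproduce.

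**Step 1. Circularity in the remission model.**
Take MRD-negative to mean the category CR without MRD. No patient can then be MRD-negative without being in remission, so that cell of the 2×2 table is 0.

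Illustration with N = 40 (the ceiling in Protocol 11.2), 46% CR (the 7+3 arm of NCI-8972, Protocol 2.6.2) and half of CRs MRD-negative (assumption):
- CRs: 40 × 0.46 ≈ 18, of which 9 are MRD-negative and 9 are not.
- No CR: 40 − 18 = 22, none MRD-negative.
- Odds ratio: (9 × 22)/(0 × 9), which is infinite.
- Adding 0.5 to each cell: (9.5 × 22.5)/(0.5 × 9.5) = 45.

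Over N = 35 to 40, CR of 46% to 70% (both arms of NCI-8972) and 30% to 60% of CRs MRD-negative (assumption), the corrected odds ratio runs from about 10 to 69. It reflects the definition and the cell sizes, not prediction.

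The separation is quasi-complete. Patients who are not MRD-negative fall in both outcome groups, because MRD-positive CR, CRi and MLFS (and PR in the wider total) also count as remission.

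**Step 2. Immortal time in the OS model.**
Null simulation: MRD has no effect, true hazard ratio (HR) 1.0, 200,000 patients per scenario.

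Inputs:
- 60-day mortality d of 4% and 10% (7+3 and FLAM, Protocol 2.6.2.3).
- Median OS M of 12, 18 and 24 months (365, 548 and 730 days), taking Protocol 1.2 as the guide.
- Censoring at 24 months (Protocol 5.6.2).
- 20% to 50% MRD-negative among patients alive at the sample (assumption; the documents give no rate).
- Patients who die before the sample coded as not MRD-negative (assumption).

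Daily hazards: h1 = −ln(1 − d)/60 up to Day 60, then h2 = (ln 2 − 60·h1)/(M − 60). For d = 10% and M = 548: h1 = 0.10536/60 = 0.001756 and h2 = (0.6931 − 0.1054)/488 = 0.001204.

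Apparent HR for MRD-negative, fixed from Day 1:

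| MRD sample | 60-day mortality 4% | 60-day mortality 10% |
|---|---|---|
| Day 14 | 0.96–0.99 | 0.90–0.95 |
| Day 50 | 0.89–0.95 | 0.73–0.87 |
| Day 60 | 0.85–0.93 | 0.68–0.85 |
| Day 180 (assumed timing after consolidation) | 0.54–0.69 | 0.49–0.61 |

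With a landmark at the sampling day, the HR is 0.98 to 1.02 in every scenario.

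**Step 3. The other coding.**
Leave out patients with no MRD result and keep Day 1 as the origin. With a common sampling day, no one in the model can die before the sample, so the partial likelihood is the same as for the landmark and the HR is about 1.0. A separate run (early deaths uniform over Days 5 to 50, half of survivors MRD-negative, median 18 months) confirms this. For 4%, 8% and 10% early deaths, the HR is about 0.88, 0.78 and 0.74 when they are coded as not negative, and about 1.0 each time when they are excluded.

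**Step 4. Size at the trial's scale.**
At n = 40, d = 10%, 40% MRD-negative and median OS of 12 to 18 months, the false-positive rate in favour of MRD-negative is 6% to 7% for a Day 60 sample and 19% to 24% for a Day 180 sample, against a nominal 2.5%. With the landmark it is 1.4% to 2.1%.

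**Step 5. The other Cox endpoints.**
RFS and CR duration start at CR. MRD taken at that same assessment is known at time zero, so no immortal time arises. It arises only if a later sample, such as one after consolidation, is entered as a fixed covariate.

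**The case against.** The strongest reply is that the SAP has already moved on. Protocol section 11 calls itself a brief overview and leaves the full detail to the SAP. The SAP models remission on baseline MCL-1 dependence, summarises the time-to-event endpoints by Kaplan-Meier, and plans no Cox or MRD-covariate table. Protocol 7.2 says that a formal efficacy analysis is not appropriate. All of this stands and keeps the point small. But the SAP nowhere says that the protocol models are dropped, and it calls the protocol its companion document, so a reader cannot tell whether they will be run.

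A second reply also stands in part. The protocol does not say how MRD will be coded, and SAP 7.2 says that missing values are in general not imputed. Its rule counting patients without marrow as non-remitters concerns response, not an MRD covariate. If unmeasured patients are left out, the OS bias is about nil. Likewise, the separation in Step 1 needs MRD-negative to mean the category CR without MRD; a quantitative MRD level would not separate in the same way. It would still be read from the sample that classifies the response.

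Third, MRD is also taken at Day 14. That sample precedes the response call, could be a legitimate early predictor, and carries little immortal-time bias. Section 11.3.2 does not restrict the covariate to Day 14.

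**Conclusion.** The point holds in limited form. As written, the remission model is circular for MRD taken at the response assessment, and its odds ratio is not estimable if MRD-negative means CR without MRD. The OS model is biased in favour of MRD-negative patients if those who die before sampling are coded as not negative: null HR about 0.7 to 0.95 for Day 50-60 MRD and about 0.90 to 0.99 for Day 14. These sizes rest on assumed MRD-negative rates and on that coding.

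A reader might infer more than the documents support:
- That the logistic model separates perfectly. It does not; the separation is quasi-complete.
- That MRD is first known at recovery, Day 50 or Day 60. It is also sampled at Day 14.
- That a spurious survival advantage is certain. It depends on a coding that neither document states.
- That RFS and CR duration share the problem. They do so only with a later MRD sample.
- That these models could show MRD predicting benefit from alvocidib. There is no control arm.

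The analyses are exploratory, and the MTD and safety objective is unaffected. The correction is still worth making, because it concerns models that the protocol states and the SAP leaves unresolved.

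**What to change.** 1. In Protocol 11.3.2, limit the remission models to dose and baseline biomarkers such as MCL-1 dependence.
2. For OS, use MRD in a landmark analysis that starts at a named MRD sampling time, or as a time-dependent covariate. Do the same for RFS or remission duration only where the MRD sample is taken after CR.
3. State in the SAP that this replaces the MRD models of Protocol 11.3.2 or, if none will be run, that they are withdrawn.

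The cost is a protocol clarification and a few sentences in the SAP. A landmark drops the patients who die before it: at 4% to 10% mortality by Day 60, about 2 to 4 of 40 (40 × 0.04 = 1.6; 40 × 0.10 = 4). A time-dependent term keeps them.

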11.3.3 Biomarker Prediction Endpoint Analyses

Summary of baseline biomarker values will include within- and between-treatment-arm descriptive statistics. If there are sufficient numbers of patients achieving remissions for an analysis to be informative, a logistic regression model will be fit to examine the relationship between baseline results and other potential biomarkers (including, but not limited to, MCL-1 dependency) and the independent binary variables complete remissions and overall remissions during the study. In addition, area under the curve (AUC) and 95% CI will be calculated (by alvocidib dose level) for the trapezoidal receiver operating characteristic curve. This value will quantify the ability of certain biomarkers (including, but not limited to, MCL-1 dependency) to predict complete/overall remissions.

11.3.4 Safety Analyses

The following safety analyses will be performed on all patients who receive at least one dose of study drug.

- **Adverse Events** = Reported adverse event (AE) terms will be mapped to MedDRA preferred terminology. All reported events will appear in AE listings, however only treatment-emergent adverse events will be summarized. A treatment-emergent adverse event (TEAE) is an AE that starts or increases in severity any time after the first administration of any study drug up to 30 days following the last administration of any study drug. AE severity will be rated by the investigator according to NCI CTCAE version 4.03.
- **Clinical Laboratory Assessments** = Laboratory test results measured on a continuous scale and changes from baseline values will be summarized by visit and within alvocidib dose level using mean, standard deviation, median, minimum and maximum values. Categorical test results will be summarized within alvocidib dose level using shift tables. Additionally, for tests where NCI CTCAE, version 4.03, severity criteria are specified, NCI CTCAE severity grades will be summarized in shift tables.

- **Vital Signs** = Vital signs and changes from baseline values will be summarized by visit and within alvocidib dose level using mean, standard deviation, median, minimum and maximum values.

